5.2 Eligibility Criteria

Inclusion Criteria:

1. **Informed consent signed** by the parent or guardian.
2. **Comply with the requirements** for executive admission.
3. **Meet the DSM-V** diagnostic impression criteria for neurodevelopmental disorders:

- Intellectual disability (ID); developmental global delay (MDR) or psychomotor delay (RPM).
 - Communication disorders: language disorders (SL), speech disorders, social communication disorder (SCD), childhood-onset dysfluency.
 - Autism spectrum disorder (ASD).
 - Attention deficit hyperactivity disorder (ADHD).
 - Motor developmental disorders: developmental coordination disorder (BDD), stereotypic movement disorder, tic disorders, Tourette's disorder (TT), chronic tic disorder (TT), transient tic disorder
 - Specific learning disorders (PAC).
4. **Respond to the GAS, Vineland-3 and FOS scales** in therapeutic admission.
 5. **Willingness of significant caregivers** to accompany in the intervention process, for twelve sessions according to the syllabus protocol.

Exclusion Criteria:

1. **Childhoods that exceed the age of 7 years** in the period of study.
2. **Children diagnosed with neurological or genetic diseases**, brain injury, visual, auditory or motor sensory deficits.
3. **Children who are under the guardianship of the Argentine State.**

6. INTERVENTION

6.1 Description of the Sentido's® Model

The intervention is based on a fidelity procedure based on three structural elements:

6.1.1 Syllabus Protocol Manual Operational systematization in seven procedural phases:

1. Executive admission.
2. Therapeutic admission.
3. GAS Administration.
4. Nutritional profile evaluation.
5. Therapeutic evaluation/probing.
6. Comprehensive therapeutic intervention.
7. Re-administration scales.

6.1.2 Professional Education and Training

- **Level 1:** Theoretical-technical training (7 modules).
- **Level 2:** Theoretical-experiential training (12 topics).
- **Level 3:** Interdisciplinary and Transdisciplinary Training Program (90 hours).

6.1.3 Physical Space and Materials

- Configuration according to neuroplasticity principles.
- 4 differentiated therapeutic environments.
- Materials categorized by developmental domains.

- Compliance with specific loyalty measures.

6.2 Intervention Mode

- **Duration:** 14 weeks.
- **Intensity:** 60 minutes daily, 4 days a week.
- **Modality:** Intensive comprehensive behavioral intervention.
- **Family inclusion:** Chaining and fading system in 12 structured sessions.

7. OUTCOME VARIABLES AND MEASURES

7.1 Primary Variable

Change in Vineland-3 Adaptive Behavior Composite Score (AUC) from baseline to week 17.

7.2 Secondary Variables

- Scores by Vineland-3 domains (Communication, Daily Life, Socialization).
- GAS scores for individualized goals.
- FOS scores for family competencies.
- Skill maintenance (week 15 vs. week 17).

8. MEASURING INSTRUMENTS

8.1 Vineland *Adaptive Behavior Scales, Third Edition* (Vineland-3)

Description: The Comprehensive Interview, Parent Form (IPPC) contains 502 items to measure five domains: Communication, Daily Living Skills, Socialization, Motor Skills, and Maladaptive Behavior.

Domains evaluated:

- **Communication:** Receptive (39 items), Expressive (49 items), Written (38 items) subdomains.
- **Daily Living Skills:** Personal (55 items), Domestic (30 items), Community (58 items) subdomains.
- **Socialization:** Interpersonal Relations (43 items), Play and Leisure (36 items), Coping Skills (33 items) subdomains.

Administration time: 10-40 minutes depending on the form and age.

Psychometric properties: Internal consistency coefficients ≥ 0.90 , test-retest reliability 0.64-0.92.

8.2 Goal Attainment Scaling (GAS)

Description: A method of personalized scales that allow quantifying progress towards specific collaboratively defined objectives.

Modified measuring system: 5-point scale adapted for EA and DND:

- -2 = current performance levels (baseline).
- -1 = progress.
- 0 = expected level of results.
- +1 = somewhat more than expected.
- +2 = much more than expected.

Conversion: Kiresuk-Sherman formula for standardized T-scores (M=50, SD=10).

8.3 Family Outcome Survey (FOS)

Description: Scale that measures results in competencies, confidence and skills of caring for families towards their children with special needs.

Administration: Caregiver self-report (15 minutes).

Internal consistency: $\alpha = 0.88$

9. STUDY PROCEDURES

9.1 Sampling Periods

Phase 1 - PRE-TEST (Baseline - Week 0):

- Control period during therapeutic admission.
- Vineland-3 administration, FOS to significant parents/caregivers.
- Elaboration of collaborative GAS objectives (parents-professionals).
- Complete interdisciplinary diagnostic evaluation.

Phase 2 - INTERVENTION (Weeks 1-14):

- Implementation of the Sentido's® Model according to the syllabus protocol.
- 4 weekly sessions of 60 minutes.
- Daily record of progress by professionals.
- Inclusion of caregivers (12 structured sessions), gradual fading of their participation in the sessions.

Phase 3 - POST-TEST (Week 15):

- Re-administration of Vineland-3, FOS, GAS evaluation after 14 weeks of intervention.
- Skills maintenance evaluation.

Phase 4 - FOLLOW-UP (Week 17):

- Third administration Vineland-3.
- Evaluation of GAS (parent-professional) objectives after two weeks without intervention.
- Post-intervention sustainability analysis.
- Return to usual intervention.

10. ETHICAL CONSIDERATIONS

10.1 Ethical and Legal Aspects

The study complies with:

- Approval of the Bioethics, Science and Technology Committee (CBCyT) of the University Institute in Health Sciences - H. A. Barceló Foundation.
- Principles of the Declaration of Helsinki.
- Standards of Good Clinical Practice.
- National Law 25,326 on the protection of personal data.
- ID code NCT06477666 in Clinical Trials.

10.2 Informed Consent

Information provided includes:

1. Objectives and importance of the project.
2. Study procedures in three time phases through scales administered by health professionals.
3. Evaluation scales used (Vineland-3, GAS, FOS) and their purpose.
4. **Voluntary participation** and right of withdrawal without penalty.
5. **Absolute confidentiality** - identity will not be revealed to any person.
6. **There will be no distinction** in the type of intervention offered, whether or not you decide to participate in the study.
7. Contact information: [name], [contact], [name] phone.
8. Contact the Ethics Committee for inquiries and/or complaints.

Specific documents:

- **Participant Information Sheet:** Complete document with details of the study.
- **Informed Consent of Parents/Legal Representative:** Formal authorization for participation.
- **Informed Assent of the Child:** Adapted document with drawings and photos for children's understanding.

10.3 Data Confidentiality

- **Coding:** Data anonymized by coding in a research file.
- **Restricted access:** Only researchers approved with professional secrecy.
- **Secure storage:** Network computers with access by personal key.
- **Transmission to third parties:** Only encrypted data with no direct identifiable information.
- **Destruction:** All data will be destroyed/deleted once the results are published.
- **Storage:** For the time necessary for research development (estimated 24 months).
- **Rights:** Participants may exercise rights of access, rectification, limitation, deletion, portability and opposition.

SECTION II: STATISTICAL ANALYSIS PLAN (SAP)

1. STATISTICAL OBJECTIVES

1.1 Primary Objective

To evaluate the statistical change in the Vineland-3 *Adaptive Behavior Composite (ABC)* composite score from baseline (week 0) to final follow-up (week 17) in participants who received intervention with the Sentido® Model.

1.2 Secondary Objectives

1. To compare scores by domains of the Vineland-3 (Communication, Daily Life, Socialization) between the three time points.
2. Evaluate changes in GAS (Goal Attainment Scaling) scores for individualized goals.
3. To analyze changes in FOS (Family Outcome Survey) scores for family competencies.
4. Determine skill maintenance between week 15 and week 17 (non-intervention period).

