4.3 Duration of the Study

- **Recruitment period:** 2023-2024.
- **Duration of individual participation:** 17 weeks.
- **Active intervention:** 14 weeks.
- **Post-intervention follow-up:** 3 weeks (3 weeks without intervention from week 15 to week 17).

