4.2 Inferential Analysis

4.2.1 Primary Variable Analysis

Main method: One-factor (time) repeated measures ANOVA with three levels.

- **Intrasubject factor:** Time (3 levels: week 0, 15, 17).
- **Dependent variable:** ABC Vineland-3 score.
- **Null hypothesis:** $H_0: \mu_0 = \mu_{15} = \mu_{17}$ (there are no differences between moments).
- **Alternative hypothesis:** H_1 : At least one mean differs.

Post-hoc comparisons: Bonferroni's method for multiple comparisons:

- Week 0 vs. Week 15.
- Week 0 vs. Week 17.
- Week 15 vs. Week 17.

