4.2.2 Analysis of Secondary Variables

Quantitative variables (Vineland-3 Domains, FOS):

- Repeated measures ANOVA (procedure identical to primary variable).
- Bonferroni correction for multiple comparisons.
- Analysis of planned contrasts (linear and quadratic).

Ordinal variables (GAS):

- Friedman's test for repeated measures ($k = 3$ moments).
- Dunn's post-hoc comparisons with Bonferroni's correction.
- Analysis by individual objective (Objective 1, 2, and 3).

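### The only inference planned on skill maintenance from week 15 to week 17 is a test of difference, which can show loss or gain but not maintenance

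*Combined protocol and SAP*

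**What the plan says.** Maintenance is a named outcome. Protocol 7.2 lists "Skill maintenance (week 15 vs. week 17") among the secondary variables, and SAP 1.2, item 4, makes it an objective: "Determine skill maintenance between week 15 and week 17 (non-intervention period").

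The inferential tools that reach these two weeks are:

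- **ABC.** SAP 4.2.1 plans a repeated measures ANOVA over weeks 0, 15 and 17. Its null is that "there are no differences between moments". Three Bonferroni pairwise comparisons follow, the last being "Week 15 vs. Week 17". SAP 4.5.2 sets each at 0.0167. SAP 5.1, Step 3, makes them conditional on a significant F.
- **Vineland-3 domains and FOS.** SAP 4.2.2 plans "Repeated measures ANOVA (procedure identical to primary variable") with Bonferroni correction, plus linear and quadratic contrasts.
- **GAS.** SAP 4.2.2 plans Friedman's test and then Dunn comparisons with Bonferroni correction.

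The SAP also plans 95% confidence intervals (4.1.1, 4.5.1), Cohen's d for pairs of means (4.6.2) and clinical change bands for the primary variable, where a change under 3 points counts as no change (5.2.1). None of these is linked to week 15 versus week 17. No margin and no definition of maintained skills is given.

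The interval without intervention is described in two ways: "3 weeks without intervention from week 15 to week 17" in protocol 4.3, and "after two weeks without intervention" in protocol 9.1, Phase 4.

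**The concern.** A test with a null of equality answers the question of whether the means differ. Rejection is evidence of loss or gain. Non-rejection is compatible with no change, but also with a real loss that the study was too small or too noisy to detect. The objective asks for the opposite kind of evidence, and the plan has no rule that supplies it. If the objective is to be answered from the planned tests, a favourable answer can come only from a non-significant p-value.

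That puts the incentive the wrong way round: lower reliability, fewer children and a stricter alpha all make non-significance more likely. The Bonferroni step, normally a protection, here makes a loss harder to detect. Protocol 1.1 names parents, policymakers and health insurers among those to be informed by the results, so a statement that gains persist without treatment could carry weight.

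**Working it through.** **Plan's own figure.** 0.05 / 3 = 0.01667, which rounds to the stated 0.0167. The documents give no power calculation for n = 24.

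**Inputs.**

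- n = 24 completers (SAP 2.2).
- SD = 15 (SAP 3.1). This is the SD of the standard-score scale; the sample SD is not given, so 15 is an assumption.
- Within-child correlation r = 0.64 to 0.92. This is the test-retest range in protocol 8.1, which is not stated to be for the ABC, so its use here is also an assumption.
- Two-sided alpha 0.05/3 with 23 degrees of freedom, critical t = 2.582.

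**Precision of the paired difference.** SD_diff = SD × √(2(1 − r)) and SE = SD_diff / √24.

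- r = 0.64: 15 × √0.72 = 12.73; SE = 2.60.
- r = 0.92: 15 × √0.16 = 6.00; SE = 1.22.

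The observed mean loss needed for significance is 2.582 × SE, which is 6.7 points at r = 0.64 and 3.2 points at r = 0.92. The 95% half-width is 2.069 × SE, which is 5.4 and 2.5 points.

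**Chance that a true loss is non-significant** (paired t-test, noncentral t with noncentrality loss / SE; for 3 points this is 3/2.60 = 1.15 and 3/1.22 = 2.45):

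| True mean ABC loss | r = 0.64 | r = 0.80 | r = 0.92 |
|---|---|---|---|
| 3 points | 90% | 83% | 54% |
| 5 points | 72% | 49% | 8% |
| 7.5 points | 38% | 11% | under 1% |

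**Sensitivity to the SD.** With a sample SD of 10, SD_diff is 10 × √0.72 = 8.49 or 10 × √0.16 = 4.00, and the 3-point figures become 78% (r = 0.64) and 15% (r = 0.92).

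**Effect of the F condition.** In a simulation of 20,000 trials with an assumed gain of 8 points from week 0 to week 15 and SD 15, a 3-point loss was detected through the gate in about 10% (r = 0.64) to 46% (r = 0.92) of trials. This is practically the same as without the gate, so the gate adds little.

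**What an interval rule would deliver.** If maintenance is concluded when the lower 95% limit of week 17 minus week 15 lies above −3 points, and there is no true loss, the rule is met with SD 15 in 20% (r = 0.64), 32% (r = 0.80) or 65% (r = 0.92) of trials. For 80% power it would need 144 children at r = 0.64 or 34 at r = 0.92.

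**The case against.** A reader might infer that the SAP equates a non-significant p-value with maintenance. It does not say so anywhere. What the documents support is narrower: the objective has no decision rule, and no planned inference could support a positive answer except non-rejection.

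The plan is also not limited to p-values. It provides confidence intervals, profile graphs, Cohen's d and change bands, and a careful analyst could use them well. That is fair, but nothing directs them to this comparison, and the bands are written for the primary variable.

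The risk is not uniform. At r = 0.92 the test rarely misses a loss of 5 points or more, and a sample SD below 15 lowers every miss rate. The 3-point case is the smallest loss that the SAP's bands count as a change. These limits stand and are shown above.

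It is tempting to extend the F condition to every outcome. SAP 5.1 states it only for the ABC; the reference to an identical procedure might carry it to the domains and FOS, but this is not explicit.

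It is also tempting to fault "Analysis of planned contrasts (linear and quadratic") on the ground that weeks 0, 15 and 17 are unequally spaced. The SAP gives no coefficients, does not say that equal steps are assumed, and does not offer these contrasts as a maintenance analysis. No error can be shown there.

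Finally, secondary outcomes are declared exploratory (SAP 4.5.2, 10.3). This moderates the weight of the point. However, the label addresses false positives, while the problem here is a missed loss. SAP 10.1 admits limited power only for subgroups.

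**Conclusion.** The point holds in this form: maintenance is a stated objective, the only inferential comparison planned for it cannot establish it, and no definition or margin fills the gap. With 24 children, SD 15 and r between 0.64 and 0.92, a 3-point ABC loss would be non-significant in 90% to 54% of trials. For larger losses the risk depends strongly on r. Both SD and r are assumptions taken from general instrument figures; with SD 10 the 3-point range is 78% to 15%. The documents do not show that the sponsor intends to read non-significance as maintenance. The reason to act is that the plan does not prevent that reading and offers no better inferential route. The change should be made, but the point does not touch the primary week 0 to week 17 analysis.

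The length of the non-intervention period is a smaller, separate matter. Three weeks and two weeks may reflect different ways of counting, but the maintenance statement refers to this interval, so protocol 4.3 and 9.1 must be reconciled.

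**What to change.** **Vineland-3.** Report the paired mean difference, week 17 minus week 15, with its 95% confidence interval whatever the F result, and state that maintenance is not concluded from a non-significant p-value. Then apply these rules in order:

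1. *Maintained* if the lower limit is above minus the margin, with the margin fixed before analysis. The 3-point limit of the SAP's no-change band is a candidate, but it was written as a descriptive label, so the sponsor should confirm or replace it.
2. Otherwise *loss* if the upper limit is below 0.
3. Otherwise *inconclusive*.

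The order matters because an interval such as −2.8 to −0.2 would satisfy both of the first two conditions. With a 3-point margin this needs a half-width below 1.5, that is SD_diff below 1.5 × √24 / 2.069 ≈ 3.6, which is unlikely but possible. Where it occurs, report the small loss within the margin alongside the conclusion.

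**GAS.** Describe the change from week 15 to week 17 with a confidence interval, for example the proportion of goals that keep or improve their level. Draw no maintenance conclusion from a non-significant Dunn test.

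**Other wording.** Reconcile the two statements of the non-intervention period. If polynomial contrasts are kept, state that they use the actual times 0, 15 and 17.

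**Cost.** SAP and protocol wording only; no new visits, data or children. The real downside is that, with a 3-point margin, SD 15 and no true loss, *maintained* would be reached in only about 20% to 65% of trials, so *inconclusive* is a likely answer. If the sponsor does not want that, the alternative is to report the estimate and interval and make no maintenance statement.

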2. STUDY DESIGN AND GENERAL CONSIDERATIONS

2.1 Type of Design

- **Design:** Prospective longitudinal intervention, pretest-posttest with follow-up.
- **Configuration:** Non-concurrent single subject design, multiple baseline.
- **Analysis:** Repeated intra-subject measures with three time points.

2.2 Population Analysis

Target population: n = 24 estimated participants who meet inclusion criteria and complete evaluations in the three planned time points.

Pre-established criteria for inclusion in analysis:

- Participants aged 3-7 years with a confirmed diagnosis of ASD and/or associated DND according to DSM-V
- Signed informed consent
- Completion of the 14-week intervention protocol
- Complete data in the three temporary evaluations

3. DEFINITIONS OF VARIABLES AND OUTCOME MEASURES

3.1 Primary Variable

Variable: Change in ABC Vineland-3 composite score.

Operational definition: Difference between ABC score at week 17 minus ABC score at week 0.

Measurement scale: Continuous (standard score with mean = 100, SD = 15).

Measurement time: Week 0 (baseline), Week 15 (post-intervention), Week 17 (follow-up).

3.2 Secondary Variables

3.2.1 Dominios Vineland-3

- **Communication:** Sum of subdomains Receptive, Expressive, Written.
- **Daily Life:** Sum of subdomains Personal, Domestic, Community.
- **Socialization:** Sum of subdomains Interpersonal Relationships, Play and Leisure, Coping Skills.
- **Scale:** Standard scores (mean = 100, SD = 15).

3.2.2 Goal Attainment Scaling (GAS)

- **Objectives 1, 2 and 3:** Individually defined by family and therapists.
- **Scale:** 5-point ordinal (-2 to +2).
- **Conversion:** T-scores using the Kiresuk-Sherman formula (mean = 50, SD = 10).

3.2.3 Family Outcome Survey (FOS)

- **Definition:** Family caregiving competencies, confidence, and skills.
- **Scale:** Continuous (total score).

3.3 Characterization Variables

- Age (full years at admission).
- Sex (male/female).
- Primary diagnosis (associated ASD, DND).
- Adherence to the protocol (percentage of completed sessions).

4. SPECIFIC STATISTICAL METHODS

4.1 Descriptive Analysis

4.1.1 Quantitative variables (Vineland-3, FOS):

- Arithmetic mean and standard deviation.
- Median and interquartile range (Q1-Q3).
- Minimum and maximum values.
- 95% confidence intervals for the mean.
- Graphical representation using boxplots and time profile graphs.

4.1.2 Ordinal variables (GAS):

- Absolute and relative frequencies by category.
- 95% confidence intervals for proportions.
- Median and quartile.
- Bar charts by time frame.

4.1.3 Categorical variables:

- Absolute and relative frequencies.
- 95% confidence intervals for proportions.

4.2 Inferential Analysis

4.2.1 Primary Variable Analysis

Main method: One-factor (time) repeated measures ANOVA with three levels.

- **Intrasubject factor:** Time (3 levels: week 0, 15, 17).
- **Dependent variable:** ABC Vineland-3 score.
- **Null hypothesis:** $H_0: \mu_0 = \mu_{15} = \mu_{17}$ (there are no differences between moments).
- **Alternative hypothesis:** H_1 : At least one mean differs.

Post-hoc comparisons: Bonferroni's method for multiple comparisons:

- Week 0 vs. Week 15.
- Week 0 vs. Week 17.
- Week 15 vs. Week 17.

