4.5 Significance Criteria and Adjustments for Multiple Comparisons

4.5.1 Level of Significance:

- **Primary analysis:** $\alpha = 0.05$ (bilateral).
- **Confidence intervals:** 95%.

4.5.2 Adjustments for Multiple Comparisons:

- **Within each variable:** Bonferroni correction for post-hoc comparisons.
- **Among secondary variables:** No adjustment (exploratory analysis).
- **Number of comparisons by ANOVA:** 3 post-hoc comparisons.

Bonferroni adjustment formula: $\alpha_{\text{ajustado}} = \alpha / \text{number of comparisons} = 0.05 / 3 = 0.0167$.

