5. SPECIFIC ANALYSIS PROCEDURES

5.1 Planned Sequence of Analysis

Step 1: Planned descriptive analysis of baseline characteristics and systematic evaluation of missing data.

Step 2: Protocolized verification of statistical assumptions for each variable according to prespecified methods.

Step 3: Planned analysis of primary variable (ABC Vineland-3):

- Repeated measures ANOVA according to protocol specifications.
- Post-hoc comparisons conditioned to significant F.
- Preset calculation of effect sizes.

Step 4: Scheduled analysis of quantitative secondary variables (Vineland-3 domains, FOS):

- Repeated measures ANOVA for each variable according to protocol.
- Post-hoc comparisons with prespecified Bonferroni correction.

Step 5: Planned ordinal secondary variable (GAS) analysis:

- Friedman's test for each objective according to design.
- Dunn's post-hoc comparisons according to protocol.

Step 6: Preset sensitivity analysis for missing data based on specified methods.

Step 7: Planned synthesis of findings and interpretation according to pre-established criteria.

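### The primary variable is the week 0 to week 17 change in ABC, but the main test is a three-mean omnibus F, and the plan does not say which result decides the primary objective

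*Combined protocol and SAP*

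**What the plan says.** Three places define the same primary quantity. Protocol 7.1 and SAP 1.1 both describe the change in the Vineland-3 composite from baseline to week 17, and SAP 3.1 gives the operational definition: "Difference between ABC score at week 17 minus ABC score at week 0".

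The analysis sections test something wider. SAP 4.2.1 names as main method a "One-factor (time) repeated measures ANOVA with three levels". Its null hypothesis is equality of the means at weeks 0, 15 and 17, and its alternative is "At least one mean differs". The comparison "Week 0 vs. Week 17" appears only as one of three post-hoc pairs. Step 3 of SAP 5.1 adds a gate, "Post-hoc comparisons conditioned to significant F", and SAP 4.5.2 applies "Bonferroni correction for post-hoc comparisons" within each variable, at 0.05/3 = 0.0167 per pair. SAP 4.5.1 sets the primary analysis at two-sided 0.05.

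Planned contrasts are listed only for the secondary variables (SAP 4.2.2), and those are linear and quadratic. No section makes week 17 minus week 0 a planned contrast at 0.05, and none states which result decides the primary objective.

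**The concern.** A primary test should answer the question set by the primary variable. Here the variable is one difference between two visits, and the test asks whether any of three means differ. What is at stake depends on how the result is read.

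- **If F is the deciding result**, the study can report a positive primary analysis driven by week 15 alone. The design makes this plausible: week 15 closes the intervention, week 17 follows a period without it, and SAP 1.2 lists maintenance between the two visits as an open question.
- **If the gated pair is the deciding result**, the defined primary change pays a three-way Bonferroni penalty. One pre-specified contrast has no multiplicity to correct, so in a study of 24 children the penalty gives power away.

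**Working it through.** **The plan's own figure.** 0.05/3 = 0.01667, which rounds to the stated 0.0167. The plan gives no target effect, SD of change or power, so there is no power figure to reproduce.

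**Inputs from the documents.** n = 24 completers (SAP 2.2); scale SD 15 (SAP 3.1); gains of 7.5 and 3 points, the lower limits of moderate and minimum change in SAP 5.2.1.

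**Assumptions.** The between-visit correlation ρ is not given. I take 0.64 to 0.92, borrowing the test-retest range in Protocol 8.1. SD 15 is the normative SD, not this sample's. The standardised change dz (mean change divided by the SD of the changes) is assumed.

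**Reading 1: F decides, and the week-15 gain g is fully lost.** The means are (0, g, 0). With equal correlations and no sphericity correction, F has 2 and 46 df, critical value 3.20, and noncentrality λ = n·Σ(μᵢ − μ̄)² / [σ²(1 − ρ)].

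- g = 7.5: Σ(μᵢ − μ̄)² = 6.25 + 25 + 6.25 = 37.5, so the numerator is 24 × 37.5 = 900.
- g = 3: Σ(μᵢ − μ̄)² = 1 + 4 + 1 = 6, so the numerator is 24 × 6 = 144.

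| ρ | σ²(1 − ρ) | λ, g = 7.5 | P(F significant) | λ, g = 3 | P(F significant) |
|---|---|---|---|---|---|
| 0.64 | 81 | 11.1 | 83% | 1.78 | 19% |
| 0.80 | 45 | 20.0 | 98% | 3.20 | 32% |
| 0.92 | 18 | 50.0 | >99.9% | 8.00 | 69% |

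The true week 17 minus week 0 difference is zero in every row, so a direct paired t at 0.05 rejects in 5%.

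The pattern does not need a total loss. In simulations of the planned procedure (100,000 trials per scenario, with the Mauchly, Greenhouse-Geisser and Huynh-Feldt steps, correlations 0.80 to 0.95), dz was 0.6 at week 15 and 0.3 at week 17. F was significant in 72% to 83% of trials, and 79% to 81% of those significant results came without a week 0 vs 17 difference at 0.0167.

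**Reading 2: the gated pair decides.** Paired t with 23 df and noncentrality dz·√24. Critical values are 2.069 at 0.05 and 2.582 at 0.0167.

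| dz | Noncentrality | Power at 0.05 | Power at 0.0167 |
|---|---|---|---|
| 0.4 | 1.96 | 47% | 29% |
| 0.5 | 2.45 | 65% | 46% |
| 0.6 | 2.94 | 80% | 64% |
| 0.7 | 3.43 | 91% | 79% |

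The change detectable with 80% power is dz 0.60 at 0.05 and 0.70 at 0.0167. Adding the F gate in simulation, with the gain maintained from week 15, gives 63% to 64% at dz 0.6 and 45% to 46% at dz 0.5. The gate therefore costs about one point at most, and the threshold accounts for the rest.

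**Power of F itself.** With equal correlations and a gain maintained at dz 0.6, λ = 11.5 and F rejects in about 85%, against 80% for the direct t. With a steady rise (0.3, then 0.6), λ = 8.64 and F rejects in 72%.

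**The case against.** The strongest reply is that the two harms belong to different decision rules. If F decides, power is not generally lost, since F can reject more often than the direct t when the gain is maintained. If the pair decides, a positive result does point to a week-17 change; in the simulated full-fade cases the gated pair was positive in under 2% of trials. This stands. A reader might infer that the plan suffers both harms at once, or that the omnibus F is simply the weaker test. Neither is supported. The defect is that the deciding result is not named, and each possible choice has its own cost.

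A reader might also infer a contradiction between 95% intervals and tests at 0.0167. SAP 4.5.1 sets the interval level without naming a parameter, and the intervals in SAP 4.1.1 are descriptive, for means. Nothing says that intervals for pairwise differences are unadjusted. This is a gap to close, not a demonstrated conflict.

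It is also fair to say that week 0 vs 17 is named in advance and would be reported after a significant F, so a faded gain would be visible. The pairwise rule is conservative and adds no type I error to that comparison. The study is descriptive in aim (Protocol 2.1) and concedes that it has no control group (SAP 10.1), so the choice of contrast does not alter the causal limits. These points reduce the practical harm, but they do not supply the missing decision rule.

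**Conclusion.** The point holds in this form: the stated main test does not answer the stated primary objective, and the plan leaves open which result does. With F as arbiter, a full fade of a 7.5-point gain still gives a positive result in 83% to nearly 100% of trials, and of a 3-point gain in 19% to 69%. With the gated pair as arbiter, power for the defined change drops by about 16 points at dz 0.6 (80% to 64%) and 19 points at dz 0.5 (65% to 46%).

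The mismatch rests on the text alone. The sizes rest on the assumed SD, correlations and dz, and the full-fade cases are deliberately extreme.

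**What to change.** In SAP 4.2.1 and in Step 3 of SAP 5.1:

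- Name the within-child contrast week 17 minus week 0 (paired t, or the equivalent model contrast) as the single primary test, at two-sided 0.05 with its 95% CI, reported whatever F shows.
- Make the omnibus F and the week 0 to 15 and week 15 to 17 contrasts secondary.
- State that any CI for those secondary contrasts uses the same level as its test.

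The paired contrast does not need the sphericity steps of SAP 4.3.1.

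**Cost.** No new data or visits are needed, only SAP wording and a few lines of syntax. SAP 8.2 classes a change of primary analysis method as a major deviation, so it needs the principal investigator's approval and a protocol amendment. The change relaxes the threshold for the week-17 comparison from 0.0167 to 0.05, so it must be made and dated before outcome data are examined. Protocol 4.4.3 places the analysis in January to September 2025, which makes that date important. The other downside is that the omnibus F is no longer the headline result.
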